#### **Exclusion criteria**

*Patients meeting any of the following criteria will not be included in the study:*

1. *Evidence of prior treatment with other CDK4/6I (Ribociclib or Abemaciclib), AI (Letrozole, Exemestane, and Anastrazole), Tamoxifen, Raloxifene, Toremifene, or Fulvestrant for MBC*
2. *First structured activity greater than 90 days after MBC diagnostic date*

#### **4.2 TREATMENT WITH A CDK4/6 INHIBITOR AS PART OF A CLINICAL TRIAL SUBGROUPS**

***Subgroup Analyses.*** *Analyses of study measures, as described above, may be repeated focusing alternatively on the following subgroups of interest—sample size permitting—which will be defined on the basis of:*

- Age (year)  
 $\leq 50$ , 51-64, 65-74, 75+
- Race  
White, Black/Asian/Hispanic/Latino
- Disease stage at initial diagnosis  
I or II, III, IV
- ECOG performance status  
0, 1 or 2,  $\geq 1$
- Site of metastasis  
Bone only, Visceral, Non-visceral
- # Metastatic sites

1, 2,  $\geq 3$

- Menopausal status
- ER/PR Status (all patients in data received from Flatiron are HR+)  
ER+/PR-, ER+PR+, ER-/PR+

**Sensitivity Analyses.** IPTW performed under Amendment I indicated an inability to adequately balance baseline variables and clinical characteristics. Propensity score matching (PSM) balanced the two cohorts, but on a reduced number of patients. Therefore, results using PSM and IPTW will be presented.

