## 6 STATISTICAL METHODOLOGY AND STATISTICAL ANALYSES

This analysis will compare effectiveness outcomes of real-world progression-free survival (rwPFS) as primary outcome and Overall survival (OS) tumor response and time to next line of anti-cancer therapy/chemotherapy as secondary outcomes (depending on the availabilities of the data) in female patients treated with Palbociclib + Letrozole as first line MBC therapy versus Letrozole alone.

Means, medians, and standard deviations will be provided for continuous variables. Counts and percentages will be provided for dichotomous and polychotomous variables. Appropriate tests (t-tests and chi-square tests) will be provided for baseline demographic and clinical characteristics.

Inverse probability treatment weighting (IPTW) will be used to balance baseline demographic and clinical characteristics and to adjust analyses for differences in observed potential confounders between the two study cohorts. The balance in important prognostic baseline characteristics will be assessed using a standardized differences approach, with values  $\geq 0.10$  indicating a non-negligible imbalance.

Propensity scores for use in IPTW will be calculated using a multivariable logistic regression model based on the following proposed baseline covariates such as age, race, practice type, type of MBC, ECOG performance score, disease stage at diagnosis (I–IV or unknown/undocumented), number of disease sites at MBC diagnosis (1, 2,  $\geq 3$ ), bone-only metastases, visceral metastases, and individual Charlson comorbidities, depending on data availability. Stabilized weights based on the propensity scores will be computed. The final list of variables to be used in the propensity score model will be discussed and determined during analysis development, after reviewing pre-matched descriptive tables. The selection of covariates for analysis will be based on the study team's clinical judgment.

The Kaplan-Meier method adjusted for weighted stabilized IPTW scores and 95% confidence intervals (CIs) will be used to estimate median rwPFS. Cox proportional hazards analyses adjusted for weighted stabilized IPTW scores will be used to estimate hazard ratios and 95% CIs for PFS.

The Kaplan-Meier method and 95% CIs will be used to estimate:

- proportions of patients surviving by cohort at follow-up years 1 through 4.

The Kaplan-Meier method adjusted for weighted stabilized IPTW scores and 95% CIs will be used to estimate:

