- median duration of treatment.

Cox proportional models with a robust sandwich estimator will be used to compare the risk of PFS and OS between the matched study cohorts. The Cox model proportionality assumption will be evaluated by visually inspecting the Kaplan-Meier plot among the matched cohorts and confirmed by testing the significance of interactions between treatment modality and the log of time as well as each time-dependent covariate and the log of time. If the proportionality assumption is violated, an interaction term of time may be added.

PSM will be performed. A multivariable binomial logistic regression model will be used to generate the propensity scores. Individual patients in the Palbociclib + Letrozole vs Letrozole alone cohorts will be matched by closest propensity scores. The Nearest Neighbor method (without replacement and with a caliper of 0.01) will be used to select the matched samples.

All data analysis will be executed using statistical software SAS version 9.4.

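### SAP Section 6 keeps a stabilized-weight Cox hazard ratio for rwPFS with no correction for covariates that stay imbalanced, although SAP 4.2 records that the weighting did not balance the cohorts

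*SAP*

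**What the plan says.** SAP 4.2, under the label for sensitivity analyses, records two findings from work already done. On weighting: "IPTW performed under Amendment I indicated an inability to adequately balance baseline variables and clinical characteristics". On matching: "Propensity score matching (PSM) balanced the two cohorts, but on a reduced number of patients". The consequence drawn is: "Therefore, results using PSM and IPTW will be presented".

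SAP Section 6 opens with the comparison of Palbociclib + Letrozole against Letrozole alone: "This analysis will compare effectiveness outcomes of real-world progression-free survival (rwPFS) as primary outcome". It still assigns IPTW the task of balancing the cohorts. On checking: "The balance in important prognostic baseline characteristics will be assessed using a standardized differences approach", with 0.10 as the level from which an imbalance counts as non-negligible. On estimation: "Cox proportional hazards analyses adjusted for weighted stabilized IPTW scores will be used to estimate hazard ratios and 95% CIs for PFS". On the propensity model: "The final list of variables to be used in the propensity score model will be discussed and determined during analysis development".

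Section 6 also specifies nearest-neighbour matching without replacement, with a caliper of 0.01, and a matched analysis: "Cox proportional models with a robust sandwich estimator will be used to compare the risk of PFS and OS between the matched study cohorts". Section 6.1 lists IPTW and PSM together for rwPFS, OS and tumor response. Its covariate column for rwPFS refers only in general terms to demographic and clinical characteristics. In Section 7, Table 1 has unweighted and weighted results, and the one rwPFS table is for IPTW.

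**The concern.** A non-randomised comparison rests on balance. The SAP sets a threshold for imbalance and records that the weighting did not balance the cohorts adequately, yet the weighted model in Section 6 takes no account of it. If the imbalance lies in prognostic variables and persists in the current data release, the weighted hazard ratio is confounded. Its confidence interval will not show this, because the interval reflects sampling error only.

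The second gap is interpretive. There will be two hazard ratios for the same primary outcome, one from an analysis recorded as inadequately balanced and one from an analysis recorded as balanced. Nothing visible tells the reader how to weigh them if they differ. SAP Section 1 says that Amendment 3.0 was prepared after the database was transferred and locked, with the primary and most secondary analyses already performed. Any unstated preference between the two would therefore be formed after results could be known.

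**Working it through.** **Step 1: the text, side by side.**
- Section 4.2: IPTW balance inadequate, PSM balance achieved, present both.
- Section 6, weighting: check standardized differences and flag 0.10 or more. No re-specification, trimming or outcome-model adjustment follows; the only flexibility is the open covariate list.
- Section 6, matching: the method and a matched Cox model for PFS and OS are specified. No step covers matched differences of 0.10 or more.
- Section 6.1: it is not stated whether the listed covariates enter the propensity model, the outcome model or both.

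**Step 2: the plan's own figure.** SAP 3.3 gives medians of 14.5 and 24.8 months, two-sided alpha 0.05, 90% power and 3.6 years of accrual, and requires 138 per group. Under exponential survival, HR = 14.5/24.8 = 0.585. With uniform accrual over 43.2 months and a further 3 months (assumed from the 90-day minimum in SAP 4.1), the event probability is 1 − [exp(−3λ) − exp(−46.2λ)]/(43.2λ), where λ = ln 2/median. This gives 0.634 and 0.466. The Lachin-Foulkes formula gives 138.1 per group. Freedman's gives 153 events, and 153/(0.634 + 0.466) = 139.1. The 138 is reproduced.

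**Step 3: what residual imbalance could do (inputs assumed).** Take one binary factor with prevalence p (30% or 50%), prognostic hazard ratio g (1.5 or 2.0) and standardized difference SMD. With d = SMD × √(p(1−p)), the approximate bias factor is

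(1 + (p − d/2)(g − 1)) / (1 + (p + d/2)(g − 1)).

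| p | g | SMD 0.10 | SMD 0.20 |
|---|---|---|---|
| 0.3 | 1.5 | 0.9803 | 0.9609 |
| 0.3 | 2.0 | 0.9654 | 0.9319 |
| 0.5 | 1.5 | 0.9802 | 0.9608 |
| 0.5 | 2.0 | 0.9672 | 0.9355 |

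The shift is 2.0-3.5% at 0.10 and 3.9-6.8% at 0.20. Applied to 0.585 in either direction, the largest shifts give 0.564 or 0.606 (×/÷ 0.9654) and 0.545 or 0.627 (×/÷ 0.9319). Simulated Cox fits that omit the factor gave 1.9-3.4% and 3.7-6.6%, so the approximation is adequate.

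SAP 4.2 speaks of variables in the plural. Two independent factors in the same direction (factors squared) give 3.9-6.8% and 7.7-13.2%; in opposite directions they partly cancel. As a harsher single case, take prevalence 30% against 44.3% (SMD 0.30) and g = 3: (1 + 0.443 × 2)/(1 + 0.30 × 2) = 1.886/1.6 = 1.18, which moves 0.585 to 0.50 or 0.69.

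**Step 4: precision for scale.** SE(log HR) = √(1/d₀ + 1/d₁), ignoring weighting variance and matched-pair correlation.

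| Per group | Events | 95% CI around 0.585 |
|---|---|---|
| 650 (SAP 3.3 count) | 412 + 303 = 715 | 0.50-0.68 |
| 325 (assumed: half matched) | 206 + 151 = 357 | 0.47-0.72 |
| 138 (SAP 3.3 requirement) | 87 + 64 = 152 | 0.42-0.81 |

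At 138 pairs, Schoenfeld power is 91% (88% with no follow-up after accrual). At 650 per group the CI multiplier is exp(1.96 × 0.0757) = 1.16, so a hazard ratio biased to 0.627 would have an upper limit of about 0.627 × 1.16 = 0.73.

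**The case against.** The strongest reply is that the plan has already acted. The imbalance was found and disclosed, matching was added, and a matched Cox model with robust variance is specified and listed in Section 6.1. This stands: a reader might infer that the imbalance was ignored or that no balanced analysis exists, and the documents show otherwise. What the reply leaves open is the weighted hazard ratio itself, which is still to be estimated without correction.

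A reader might also infer from Section 7 that IPTW is the intended main result. The list does not support that. It has no table for tumor response, time to next line, time to chemotherapy or dose, all of which Section 6.1 plans. It is plainly incomplete, and a missing matched table says little about intent.

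A third tempting reading is that PSM must lead. The documents do not establish this. The number of matched pairs is not given, and a 0.01 caliper could retain few. The matched population is a different target from that of stabilized weights. The covariate list is open, so the recorded balance need not carry over to the current release. A ranking chosen now would come after lock. Statisticians could reasonably differ on it, and presenting both is defensible.

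Finally, a ranking may sit in redacted text (the SAP objective and hypotheses, and parts of Protocol 9.7). The Section 6.1 covariate column may also be meant as outcome-model adjustment, but it does not say so.

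**Conclusion.** The point holds in limited form. Followed as written, Section 6 yields a weighted rwPFS hazard ratio from a method the SAP records as inadequately balanced. No correction is tied to its own 0.10 threshold, and no visible rule says how to read that estimate beside the matched one.

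The size is modest under the assumed inputs: about 2-7% on the hazard ratio for one factor at a standardized difference of 0.10-0.20, up to about 13% for two aligned factors, and about 18% in the harsher single case. The actual differences and the number of matched pairs are undocumented. A reader might infer that the comparison could be reversed. One factor of the size assumed would not overturn an effect near 0.585, since even 0.627 keeps an upper limit well below 1. A true effect closer to 1 would be more exposed. SAP Section 1 ties the comparative methods to an exploratory objective, and Protocol 9.9 disclaims causal inference. Both limit the weight of the point, but neither is a reason to leave the correction out.

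**What to change.** In SAP Section 6, with matching changes in Section 7:

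1. In the weighted Cox model for rwPFS, include every baseline covariate whose post-weighting standardized difference is 0.10 or more. Apply the same rule to the matched Cox model with post-matching differences.
2. Report standardized differences after weighting and after matching, the number of matched pairs, and the PSM rwPFS hazard ratio beside the IPTW one. State that an IPTW estimate failing the 0.10 criterion is not to be read as the main result without the adjusted and matched results.
3. If one estimate is named as lead, base the choice on balance in the current data release, state its target population, and label the choice as made after database lock.

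The cost is SAP wording, the adjusted Cox fits, a matched column in Table 1 and one PSM rwPFS table. The data are in hand and matching is already planned. There are two downsides. The adjusted hazard ratio is conditional, so it does not estimate quite the same quantity as the marginal weighted one. The matched estimate uses fewer patients and describes the matched population; if half of 650 per cohort matched, its interval would be about 0.47-0.72 rather than 0.50-0.68.

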## 5 ENDPOINTS AND COVARIATES

Demographic and clinical characteristics and clinical outcomes including PFS and OS will be compared between patients who were treated with first line Palbociclib + Letrozole versus first line Letrozole alone.

### 5.1 EFFICACY/ EFFECTIVENESS ENDPOINT(S)

*All variables are assessed or defined by Flatiron using business rules before and after first line Palbociclib + Letrozole or first line Letrozole alone initiation*

Variable	Operational definition
Demographic characteristics	
Age	Age at MBC diagnosis, years
Age category	$\leq 50$ , 51-64, 65 –74, $\geq 75$ years
Race	White, Black, Asian, other, unknown
Region of residence	Based on state where the patient resides: Northeast, Midwest, South, West
Practice type	Academic, community
Insurance type	Commercial, Medicare, Medicaid
Duration of follow-up	Months from the index date to the date of death, or the data cutoff date, whichever came first.
Clinical characteristics	
Type of MBC	De novo MBC (newly diagnosed): Stage 4 at initial BC diagnosis Recurrent MBC: Stages 0-3 at initial BC diagnosis
ECOG performance score	ECOG performance at index date, 0, 1, 2, 3, 4
Disease stage at initial BC diagnosis	Stage I, II, III, IV, unknown/ undocumented
Time from initial BC diagnosis to first MBC diagnosis	Months from the date of initial BC diagnosis to the date of metastatic diagnosis

Time to treatment discontinuation	
 
The time from the start of a treatment to the time of treatment discontinuation for any reason in 1LOT
 
Start date: PAL/AI start date in 1LOT
 
End date: 
 
A. PAL/AI end date in 1LOT
 
B. 2LOT start date
 
C. Death date in 1LOT
 
D. Whichever came first
 
 
 
Censoring date: latest available drug administration or latest visit/activity date (lab, office, radiology, etc), end of study, or loss to follow-up, whichever came first.
 
2LOT start date 
 
A. Start date of adding any new anti-neoplastic (chemotherapy, target therapy (eg., Abemaciclib, Ribociclib), or endocrine therapy) if there is evidence of disease progression or after 60 days of index date if there is no evidence of disease progression.
 
B. AI discontinuation or exchange from one AI to another AI is not considered as 2LOT start if there is no evidence of disease progression
 
C. Exchange from one PAL to another CDK4/6i AI is not considered as 2LOT start if there is no evidence of disease progression.
 
D. 1LOT was not advanced if PAL and/or AI were paused or stopped and then restarted within 120. Different days (90, 120, and 180) will be used as sensitivity analyses.
 
 
 

Organ-level metastatic sites	Number of sites; Sites of metastases (bone, lung, liver, brain, distant lymph nodes, other) Visceral vs. non-visceral, bone only
Modified Charlson comorbidity index (CCI)	As defined in the Flatiron database
Effectiveness outcomes	
Overall survival (OS)	
Time in months from index date to death due to any cause or censoring date will be calculated.
 
Based on an improved understanding of the death information in Flatiron and a better understanding of the OS analysis in PALOMA-2 the following changes will be made to the OS outcome definition.
 
Event: Any death recorded by Flatiron in the data extract. Patients who did not die will be censored at the time of data cutoff.

Real-world PFS (rwPFS)	
Time in months from index date to progression or censoring date will be calculated.
 
Based on improved understanding of the PFS analysis in PALOMA-2 the following changes will be made to the PFS outcome definition.
 
Event: Any death or disease progression (concluded by the treating clinician based on radiology, laboratory evidence, pathology, or clinical assessment). If patients did not die or have disease progression, they were censored at the date of initiation of next line of therapy for patients with two or more lines of therapy or their last visit date during the study period for patients with only one line of therapy.

Real-world tumor responses (rwTR)	
 
● Complete response: complete resolution of all visible disease.
 
● Partial response: partial reduction in size of visible disease in some or all areas without any areas of increase in visible disease.
 
● Stable disease: no change in overall size of visible disease; also included cases where some lesions increased in size and some lesions decreased in size
 
● Progressive disease: an increase in visible disease and/or presence of any new lesions; included cases where the clinician indicated progressive disease.
 

Response rate	
 
● Complete response or partial response divided by the number of patients with at least one tumor assessment while on the index treatment.
 

Time to next line of anti-cancer therapy	
 
● Defined as the time from the initiation of 1LOT (PAL+AI) until either 
 
○ the day before the start of 2LOT for patients with evidence of 2LOT, or
 
○ death if the death occurred within 60 days following the patient's last administration of 1LOT (PalB/AI)
 
○ Whichever occurred first.
 
 
 
● If a patient did not have evidence of 2LOT and did not die within the 60 days following the last 1LOT administration, the patient was censored at the latest available date that occurred on or before the end of study date of either last drug administration plus the number of days in a treatment cycle (last PAL/AI administration + 28 days) last visit date (e.g., office visit, lab, radiology, etc), or data cutoff date.
 

Time to chemotherapy	
 
Defined as the time from the initiation of 1LOT PAL+AI until either 
 
The day before the start of subsequent chemotherapy for patients with evidence of chemotherapy, or
 
Death for any reasons
 
Whichever came first
 
 
 
If a patient did not have evidence of subsequent chemotherapy and did not die, the patient was censored 
 
at the last visit date (e.g, office visit, lab, radiology), or
 
data cutoff date
 
whichever came later
 
 
 

Initial dose of Palbociclib	
 
Index dose level of Palbociclib: 125mg, 100mg, or 75 mg
 

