| Lines of therapy | Lines of therapy in the metastatic setting are assigned by Flatiron to evaluate systemic treatment on or after the MBC date |
| Initial prescribed dose | Palbociclib: 125mg, 100mg, 75mg using |
| Dose adjustment | Dose strength other than initial/previous prescription |
| Type of the first dose change | Dose reduction 125mg to 100mg, 125mg to 75mg, 100mg to 75mg Dose increase 75mg to 100mg, 100mg to 125mg, 75 mg to 125 mg |
| Time to the first dose change | Days from index date to first dose change |
| Number of dose adjustment | Number of dose reduction and number of dose increase over the calendar time (quarter since February 2015) and over treatment cycle since index date |
| Reasons for dose adjustment | As categorized by Flatiron |
| Reasons for discontinuation | Disease progress, toxicity, financial, patient request, other |
| Duration of treatment | Days from index prescription order date to end of treatment |
| Combination endocrine partner | Letrozole, Anastrozole, Exemestane |
| Concomitant LHRH Agonists | Goserelin (Zoladex), Histrelin (Vantas), Leuprolide (Eligard, Lupron), Triptorelin (Trelstar) |
| Other concomitant anti-cancer therapies | Chemotherapy (See Table 2 for detail) |
| Effectiveness outcomes | |
| Real-world PFS (rwPFS) | Months from index date to death or disease progression (growth or worsening in the disease concluded by the treating clinician based on radiology, laboratory evidence, pathology, or clinical assessment) whichever came first. If patients did not die or have disease progression, they were censored at the date of initiation of next line of therapy for patients with two or more lines of therapy or their last visit date during the study period for patients with only one line of therapy |
| Overall survival (OS) | Months from index date to the date of death. Patients who did not die period are censored at the time of data cut-off |

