9.8. Quality Control

This is a retrospective study, so issues of quality control at study sites, eg, data clarification queries, do not apply. Analyses are programmed according the specifications in the protocol's SAP and all code and other technical artifacts are documented and stored following established programming practices on Pfizer servers and in Pfizer's Global Document Management System. Quality control (QC) will follow the Flatiron's standard procedure for quality control and assurance as described in Flatiron Health Analytic Database Parent Protocol. QC for structured and unstructured data is conducted prior to delivery of each dataset. For each data model, Flatiron generates and continually maintains a set of quality standards and versioned business rules. These QC standards cover themes such as demographics, biomarkers, treatment, therapy shares, treatment length/dosage, lines of therapy, real world recurrence, and real world progression free survival. They have a team of 900 expert nurse and physician abstractors that co-create and version rules, and also to create QC that includes both medical considerations (eg, what are expected based on the literature and clinical practice) and data considerations (eg, stability from prior months). Missingness of death data is a major confounding factor for many real-world oncology analyses. For survival data, Flatiron Health utilizes four resources, including the National Death Index, US Social Security Death Index, obituaries and commercial death data published from a vendor to identify when patients have died

(<https://onlinelibrary.wiley.com/doi/full/10.1111/1475-6773.12872>). In a study of advanced non-small cell lung cancer patients, sensitivity increased from 66% from Flatiron's HER-based registry alone to over 91% from the composite of the four sources.

QC will be performed for the results of the study, including reviewing and double checking for correct data, consistency, spelling, grammar and structure. It is also reviewed to ensure that it conforms to Flatiron's data dictionary, has internal consistency (eg, that date of diagnosis occurs after date of birth) and meets the study objectives. The final review of the findings and content will be conducted in a summary presentation.

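### rwPFS counts a death at any distance after the last visit but censors single-line survivors at that visit; a windowed sensitivity analysis with late-death counts is missing

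*SAP*

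**What the plan says.** - **Event.** SAP 5.1: "Event: Any death or disease progression (concluded by the treating clinician based on radiology, laboratory evidence, pathology, or clinical assessment". Protocol Table 1 (section 9.3) has the same rule: "Months from index date to death or disease progression". Neither limits the interval between last contact and death.
- **Censoring.** SAP 5.1: "If patients did not die or have disease progression, they were censored at the date of initiation of next line of therapy" if there are two or more lines, "or their last visit date during the study period for patients with only one line of therapy".
- **Where the events come from.** Protocol 9.8: "Flatiron Health utilizes four resources, including the National Death Index, US Social Security Death Index, obituaries and commercial death data published from a vendor". It cites a lung cancer study in which sensitivity for death rose from 66% (EHR-based registry alone) to over 91% (composite). SAP 2.1 says the mortality file holds only month and year of death. The progression file holds the date of the last clinic note and the progression dates taken from the chart.
- **Other endpoints in SAP 5.1.** OS counts any death and censors survivors at data cutoff. Time to chemotherapy counts any death and censors at the later of last visit and cutoff. Time to next line counts "death if the death occurred within 60 days following" the last first-line administration.
- **Role.** rwPFS is the primary outcome (SAP 6; Protocol 9.1). Protocol 9.7 lists 24, 30 and 36 months among its landmarks.
- **Sensitivity analyses.** Protocol 9.7 plans a subset with at least three palbociclib prescriptions and one with at least 6 months of follow-up. SAP 4.2 plans PSM alongside IPTW. None of these concerns deaths after loss of contact.

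**The concern.** Progression is seen only while a woman attends; death can be learned afterwards from outside sources. Take a woman on her only line of therapy who is last seen at month 8. If she dies at month 30, she is an rwPFS event at month 30 and 22 unobserved months count as progression-free. If she is alive at cutoff, she is censored at month 8.

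Deaths from the unobserved period therefore enter the numerator, while equally unobserved survivors have left the risk set. Censoring that depends on later vital status is not the non-informative censoring that Kaplan-Meier and Cox assume. At stake are the late landmarks of the primary outcome and, if loss differs between cohorts, the hazard ratio.

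**Working it through.** **1. The plan's own figure.** SAP 3.3 requires 138 per group, from medians of 14.5 and 24.8 months, two-sided alpha 0.05, 90% power and 3.6 years (43.2 months) of accrual. The exponential hazard ratio is 14.5/24.8 = 0.585. The Lachin-Foulkes formula with 3 further months of follow-up gives 138.1, so the figure reproduces. It does not depend on the rule discussed here.

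**2. Reference values.** Exponential rwPFS at 36 months is 2^(−36/24.8) = 36.6% for palbociclib + letrozole and 2^(−36/14.5) = 17.9% for letrozole.

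**3. Loss unrelated to progression.** The loss rate, share of deaths without progression and survival after progression are assumptions; the documents give none of them. All simulated patients are single-line.

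- Model A: 5% of PFS events are deaths without progression; median survival after progression 24 months; 91% of deaths after loss captured; follow-up uniform over 3 to 45.9 months.
- Model B: 10% of PFS events are such deaths; 20 months; all deaths captured; visit gap 0 to 1.5 months; follow-up uniform over 3 to 46.2 months.

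36-month rwPFS, palbociclib/letrozole (%):

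| Model | Loss per year | Full observation | As written | Drop (points) |
|---|---|---|---|---|
| A | 10% | 36.6/17.9 | 34.9/16.9 | 1.7/1.0 |
| A | 20% | 36.6/17.9 | 33.2/15.6 | 3.4/2.3 |
| B | 10% | 36.6/17.8 | 34.3/16.2 | 2.3/1.6 |
| B | 20% | 36.7/17.7 | 31.9/14.4 | 4.8/3.3 |

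The harshest variant (model B with 10-month survival after progression, 20% loss) gives 29.9/13.8 against 36.6/18.1, a drop of 6.7/4.3 points. Deaths more than 60 days after last contact make up 3% (10% loss) or 6% (20% loss) of events in model A, and 8 to 9% in model B at 20% loss.

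Earlier quantities move less. In model A at 10% loss, 24-month rwPFS is 50.8 against 51.2 (palbociclib) and 31.6 against 31.7 (letrozole). In model B the palbociclib median is 24.2 against 24.8 months at 10% loss and 23.8 against 24.9 at 20%; the letrozole median rises by about 0.1 month. Progression missed in the gap is replaced by a later death, which offsets part of the effect.

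**4. Hazard ratio (model B, as written against full observation).**

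- Equal loss: 0.588 against 0.583 (10%); 0.591 against 0.581 (20%).
- Letrozole 10%, palbociclib 20%: 0.610 against 0.587, a shift of +0.023.
- Letrozole 20%, palbociclib 10%: 0.578 against 0.585, a shift of −0.007.
- Largest shift across the variants run: 0.618 against 0.587, or +0.031.

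**5. Loss because of progression.** Model A with 10% random loss per year, plus a fraction of progressors who leave just before progression is charted and then have a 6-month median survival. 36-month rwPFS, palbociclib/letrozole (%):

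| Fraction leaving | Full observation | As written | 60-day window |
|---|---|---|---|
| 0% | 36.5/17.8 | 35.0/16.8 | 36.5/17.8 |
| 5% | 36.5/17.9 | 35.4/17.2 | 37.9/19.1 |
| 10% | 36.6/18.0 | 35.8/17.5 | 39.4/20.6 |
| 20% | 36.6/17.9 | 36.6/18.1 | 42.8/23.4 |

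At fractions of 5 and 10% the window reads high by 37.9 − 36.5 = 1.4 and 39.4 − 36.6 = 2.8 points (palbociclib), and by 1.2 and 2.6 points (letrozole). With 20% random loss and a 10% fraction, palbociclib is 36.5 under full observation, 33.3 as written and 39.3 with the window.

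**The case against.** A reader might infer that the any-death rule should be replaced by a 60-day window, which under random loss restores almost exactly the full-observation curve. The documents do not support that step. For a woman who stops attending because she is progressing, the later death may be the only trace of a true PFS event, and the window deletes it. At 10% random loss per year, the window is already the more biased of the two once about 5% of progressors leave this way. The documents give neither rate.

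A reader might also take the 60 days in time to next line as the plan's own precedent. That limit runs from the last first-line administration, not the last clinic note. SAP 6.1 says that outcome is not meant to measure effectiveness, and Protocol Table 1 defines the same outcome with death from any cause and no limit. Month-only death dates would also misclassify some deaths around a 60-day cut.

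The third objection is size. With the 1,221 and 627 patients in Protocol 9.5, the standard error of the log hazard ratio is about 0.07. The 95% interval is then 0.585 × exp(±1.96 × 0.07), or 0.51 to 0.67, so a shift of 0.03 lies well inside it. At 36 months the drop at 10% loss in model A is below one standard error (about 2.2 to 2.4 points).

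Finally, SAP 5.1 adopted the event rule deliberately, citing PALOMA-2. SAP 1 records that the database was locked and the primary analysis done before Amendment 3.0.

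All of this stands against changing the primary rule. It does not remove the asymmetry, and no planned output would show how many events are late deaths.

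**Conclusion.** The asymmetry follows from the text of both documents: a single-line patient's time at risk depends on later vital status. If loss is unrelated to progression, the effect falls mainly on the 30- and 36-month estimates. At 36 months it is about 1 to 1.5 points at 10% loss per year and 2.5 to 3.5 points at 20% (model A, rounded). Model B and its variants give larger drops, up to 6.7 points. Effects on 24-month values and medians are small in model A; the largest median change in any variant was about 1.7 months, in the palbociclib cohort. The hazard ratio moves by about 0.00 to 0.03, either way.

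A reader might infer that the primary comparison is unreliable or that all estimates from 24 months on are materially too low. Neither follows from these figures, which all rest on assumed loss rates.

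Read literally, the same dependence applies to women who start a second line without recorded progression; that group is not sized here.

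**What to change.** Keep the any-death rule as primary. In SAP 5.1 and 6, add one sensitivity analysis labelled post hoc:

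- Count death as an rwPFS event only within a stated window after the last clinic note; otherwise censor at that note.
- Define the window in whole months, for example 2 and 3, because only month and year of death are available.
- Report the number of deaths beyond the window in each cohort.
- Interpret the 30- and 36-month landmarks and the hazard ratio in light of both versions.

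The cost is a short SAP addition and one re-run; the mortality and progression files in SAP 2.1 already hold the fields. The downside is the upward reading in step 5, about 1 to 3 points at 36 months if 5 to 10% of progressors leave because of progression. The report should therefore present the two versions as a range under opposite assumptions about loss.
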